5.3 Meals and Dietary Restrictions

1. Participants should refrain from consumption of any nutrients known to modulate CYP enzyme activity (e.g., grapefruit or grapefruit juice, pomelo juice, star fruit, pomegranate, and Seville or Moro [blood] orange products) within 72 hours before the first dose of study drug and during the study.
2. Diet should be generally stable during the study, e.g., new diet programs should not be initiated.

5.4 Caffeine, Alcohol, and Tobacco

1. During the outpatient portions of the study, participants should refrain from more than 2 standard units per day of alcohol for men or 1 unit/day for women, consumed no less than 3 hours prior to bedtime. Alcohol should not be consumed on PSG nights.
2. Moderate consumption of caffeinated beverages, containing up to a total of 400 mg caffeine per day, is permitted during the study period, consumed no less than 3 hours prior to bedtime.

5.5 Activity

There are no restrictions on physical activity during the study other than that physical activity should be generally stable during the study (e.g., new exercise programs should not be initiated).

5.6 Screen Failures

Screen failures are defined as participants who consent to participate in the clinical study but are not subsequently assigned to receive study treatment/entered into the study. A minimal set of screen failure information is required to ensure transparent reporting of screen failure participants that meets the Consolidated Standards of Reporting Trials publishing requirements and to respond to queries from regulatory authorities. Minimal information includes demography, screen failure details, eligibility criteria, and any serious adverse events (SAEs).

Individuals who do not meet the criteria for participation in this study (screen failure) will not be rescreened, except if the opportunity for rescreening has been enabled by protocol amendment.

6 Study Drug

Study drug is defined as any investigational treatment(s), marketed product(s), placebo, or medical device(s) intended to be administered to a study participant according to the study protocol.

6.1 Study Treatment(s) Administered

One capsule of atomoxetine (week 1) or one capsule of atomoxetine and one capsule of dronabinol (weeks 2-4) is taken immediately before the participant's planned bedtime.

Study Treatment Name:	Atomoxetine hydrochloride	Dronabinol
Dosage Formulation:	Capsule	Capsule
Dosage Levels:	40 mg, 80 mg	2.5 mg, 5 mg, 10 mg
Route of Administration:	Oral	Oral
Dosing Instructions:	1 capsule administered with up to 240 mL water	1 capsule administered with up to 240 mL water
Storage/Packaging/Labeling:	Store at room temperature, in HDPE bottles	Store at room temperature in HDPE bottles

6.2 Preparation/Handling/Storage/Accountability

1. The Investigator or designee must maintain a log to confirm appropriate temperature conditions have been maintained during transit for all study treatments received and any discrepancies are reported and resolved before use of the study treatment.
2. Only participants enrolled in the study may receive study treatments and only authorized site staff may supply or administer study treatments. All study treatments must be stored in a secure, environmentally controlled, and monitored (manual or automated) area in accordance with the labeled storage conditions with access limited to the Investigator and authorized site staff.
3. The Investigator, institution, or the head of the medical institution (where applicable) is responsible for study treatment accountability, reconciliation, and record maintenance (i.e., receipt, reconciliation, and final disposition records).

4. After receiving Sponsor approval in writing, sites are responsible for returning all unused or partially used study treatment to the Sponsor or designated third party or for preparing the study treatment for destruction via incineration.

6.3 Concomitant Therapy

Concomitant therapy with the medications listed below is disallowed. For medication that is typically used as-needed for symptomatic conditions (e.g., occasional use of a sleep aid), the medication should not be used for at least one week prior to the first study PSG and for the duration of the study.

- MAOIs or other drugs that affect monoamine concentrations (e.g., rasagiline) [MAOIs are contraindicated for use with atomoxetine]
- Lithium
- Cannabinoids
- Selective Serotonin Reuptake Inhibitors (e.g., paroxetine)
- Selective Norepinephrine Reuptake Inhibitors (e.g., duloxetine)
- Norepinephrine Reuptake Inhibitors (e.g., reboxetine)
- Alpha-1 antagonists (e.g., tamsulosin)
- Tricyclic antidepressants (e.g., desipramine)
- CYP2D6 inhibitors
- Strong CYP3A4 inhibitors (e.g., ketoconazole)
- Benzodiazepines and other anxiolytics
- Opioids
- Sedatives and sedative-hypnotics, including nonbenzodiazepine “Z-drugs” (zolpidem, zaleplon, eszopiclone)
- Muscle relaxants
- Pressor agents
- Drugs with clinically significant cardiac QT-interval prolonging effects
- Drugs known to lower seizure threshold (e.g., chloroquine)
- Amphetamines

- Antiepileptics
- Antiemetics
- Modafinil or armodafinil
- Beta₂ agonists, (e.g., albuterol)
- Antipsychotics
- Sedating antihistamines
- Pseudoephedrine, phenylephrine, oxymetazoline
- Nicotine replacement products
- Most drugs for Parkinson's, Alzheimer's, Huntington's, Amyotrophic Lateral Sclerosis, or drugs for other neurodegenerative diseases

Medications that do not have substantial effects on the central nervous system (CNS), respiration, or muscle activity are generally allowed including, but not necessarily limited to, the following drugs and drug classes:

- Antihypertensives (angiotensin-converting-enzyme [ACE] /angiotensin II receptor blocker [ARB] inhibitors, calcium channel blockers, hydrochlorothiazide, etc.).
- Statins
- Proton pump inhibitors and histamine h₂ receptor blockers
- Over-the-counter (OTC) antacids
- Non-sedating antihistamines (e.g., cetirizine, loratadine)
- Acetaminophen
- Laxatives
- Erectile dysfunction drugs
- Inhaled corticosteroids (e.g., fluticasone)
- Anti-diabetics
- Ocular hypotensives and other ophthalmics (e.g., timolol)
- Hormonal therapy (e.g., estrogen replacement or anti-estrogens) and hormonal contraceptives

- Thyroid medications
- Anticoagulants
- Osteoporosis drugs

6.4 Discontinuation of Study Treatment

If a clinically significant finding is identified, the Investigator or qualified designee will determine if the participant can continue in the study and if any change in participant management is needed. Any new clinically relevant finding should be reported as an adverse event (AE).

6.5 Stopping Criteria

6.5.1 Individual Participant Stopping Criteria

- Incidents of abuse, diversion, or misuse of the study treatment.
- Incidents of clinical significance: hallucinations, amnesia, delusional thinking, delirium, manic symptoms, aggressive behavior, suicidality, homicidality, agitation, confusion, or convulsions/seizures.
- Participants reporting any SAE considered possibly related or related to study treatment.
- Any other AE that in the judgment of the Investigator necessitates the participant stopping to protect participant safety.

Participants discontinued from dosing will undergo end of study procedures with follow-up monitoring of any AE(s) as clinically indicated.

6.6 Participant Discontinuation/Withdrawal from the Study

- A participant may withdraw from the study at any time at his/her own request, or may be withdrawn at any time at the discretion of the Investigator for safety, behavioral, or administrative reasons.
- If the participant withdraws consent for disclosure of future information, the Sponsor may retain and continue to use any data collected before such a withdrawal of consent.
- If a participant withdraws from the study, he/she may request destruction of any samples taken and not tested, and the Investigator must document this in the site study records.

- All participants who withdraw from the study with an ongoing AE must be followed until the event is resolved or deemed stable.
- Participation may be terminated before completing the study and the reason recorded as follows:
 - Withdrawal due to AE
 - Withdrawal due to incident abuse, diversion, or misuse of the study treatment
 - Loss to follow-up
 - Participant withdrew consent at own request
 - Other

6.7 Loss of Participants to Follow-Up

A participant will be considered lost to follow-up if he or she repeatedly fails to return for scheduled visits and is unable to be contacted by the study site. The following actions must be taken if a participant fails to return to the clinic for a required study visit:

- The site must attempt to contact the participant and reschedule the missed visit as soon as possible (and within the visit window, where one is defined) and counsel the participant on the importance of maintaining the assigned visit schedule and ascertain whether or not the participant wishes to and/or should continue in the study.
- In cases in which the participant is deemed lost to follow-up, the Investigator or designee must make every effort to regain contact with the participant (where possible, 3 telephone calls and, if necessary, a certified letter to the participant's last known mailing address or local equivalent methods). These contact attempts should be documented in the participant's medical record/eCRF.
- Should the participant continue to be unreachable, he/she will be considered to have withdrawn from the study.

7 Study Assessments and Procedures

- Study procedures and their timing are summarized in the SoA.
- Adherence to the study design requirements, including those specified in the SoA, is essential and required for study conduct.
- All screening evaluations must be completed and reviewed to confirm that potential participants meet all eligibility criteria. The Investigator will maintain a screening log to record details of all participants screened and to confirm eligibility or record reasons for screening failure, as applicable.
- The maximum amount of blood collected from each participant over the duration of the study will not exceed approximately 50 mL.
- Repeat or unscheduled samples may be taken for safety reasons or for technical issues with the samples, as per the Investigator or designee's discretion.

7.1.1 Polysomnography

- Methods: Standard overnight PSG recording and data interpretation will be performed in accordance with the American Academy of Sleep Medicine (AASM) scoring manual. Participants will be instrumented with standard PSG electrodes. Time of lights out will be established according to the participants' habitual schedule and kept constant across the PSG study nights. The participants will be given 8 hours of time-in bed.
- Participants should be actively encouraged to spend at least 1/3 of the night in the supine position and at least 1/3 of the night in the lateral position on each night of study.

7.2 Safety Assessments

- Planned time points for all safety assessments are provided in the SoA.
- Safety monitoring will be guided by the established safety profiles of dronabinol and atomoxetine. Safety assessments will include physical examinations, measurement of vital signs, DSST, VOLT, PVT, monitoring and recording of AEs, SAEs, and pregnancies, recording of study or treatment discontinuations. Effects on OSA and sleep parameters (e.g., sleep time and sleep stages) will also be monitored by PSG.

7.2.1 Physical Examinations

- The general physical examination at screening includes an assessment of general appearance and a review of physical systems (dermatologic, head, eyes, ears, nose, mouth/throat/neck, thyroid, lymph nodes, respiratory, cardiovascular, gastrointestinal, extremities, musculoskeletal, neurologic, and psychiatric systems). Height and weight will also be measured and recorded (with shoes removed and wearing light indoor clothing).
- Investigators should pay special attention to clinical signs related to previous serious illnesses.

7.2.2 Vital Signs

- Assessment of vital signs (seated blood pressure, pulse rate, body temperature, respiratory rate) will be performed at the time points indicated in the SoA.
- Vital signs will be measured at all visits in a seated position after 5 minutes rest and will include temperature, respiratory rate, systolic and diastolic blood pressure, and pulse. Measurements should be made in the same arm of the participant at each visit.
- Systolic and diastolic blood pressure will be repeated for a total of 3 measurements, each at least 2 minutes apart.

7.2.3 Electrocardiograms

- A 12-lead ECG will be obtained using an ECG machine that automatically calculates the heart rate and measures the PR, QRS, and QT intervals. The ECG will be recorded in the semi-supine position after the participant has rested in this position for at least 10 minutes.

7.2.4 Clinical Safety Laboratory Assessments

- Refer to Section 9.2 for the list of screening clinical laboratory tests to be performed and to the SoA for the timing and frequency.
- The Investigator must review the laboratory report and document this review. The laboratory reports must be filed with the source documents.
- All protocol-required laboratory assessments must be conducted in accordance with the laboratory manual and the SoA.

- If laboratory values from laboratory assessments not specified in the protocol and performed at the institution's local laboratory result in the need for a change in participant management or are considered clinically relevant by the Investigator (e.g., are considered to be an SAE or an AE or require dose modification), then the results must be recorded in the eCRF.

7.3 Adverse Events and Serious Adverse Events

The definitions of AEs and SAEs can be found in Appendix 3. Adverse events will be reported by the participant (or, when appropriate, by a caregiver, surrogate, or the participant's legally authorized representative).

The Investigator and any qualified designees are responsible for detecting, documenting, and reporting events that meet the definition of an AE or SAE and remain responsible for following up on AEs that are serious, considered related to the study treatment or the study, or that caused the participant to discontinue the study and/or study treatment.

7.3.1 Time Period and Frequency for Collecting AE and SAE Information

All AEs and SAEs will be collected from first dose of study drug until the end of the study at the timepoints specified in the SoA.

All SAEs will be recorded and reported to the Sponsor or designee within 24 hours, as indicated in Appendix 3. The Investigator will submit any updated SAE data to the Sponsor within 24 hours of it being available.

Investigators are not obligated to actively seek AEs or SAEs after the conclusion of study participation. However, if the Investigator learns of any SAE, including a death, at any time after a participant has been discharged from the study, and he/she considers the event to be reasonably related to the study treatment or study participation, the Investigator must promptly notify the Sponsor.

The method of recording, evaluating, and assessing causality of AEs and SAEs and the procedures for completing and transmitting SAE reports are provided in Appendix 3.

7.3.2 Method of Detecting AEs and SAEs

Care will be taken not to introduce bias when detecting AEs and/or SAEs. Open-ended and non-leading verbal questioning of the participant is the preferred method to inquire about AE occurrence.

7.3.3 Follow-up of AEs and SAEs

After the initial AE/SAE report, the Investigator is required to proactively follow each participant at subsequent visits/contacts. All SAEs will be followed until resolution, stabilization, until the event is otherwise explained, or the participant is lost to follow-up. Further information on follow-up procedures is given in Appendix 3.

7.3.4 Regulatory Reporting Requirements for SAEs

- Prompt notification (within 24 hours, see Appendix 3) by the Investigator to the Sponsor of an SAE is essential so that legal obligations and ethical responsibilities towards the safety of participants and the safety of a study treatment under clinical investigation are met.
- The Sponsor has a legal responsibility to notify both the local regulatory authority and other regulatory agencies about the safety of a study treatment under clinical investigation. The Sponsor will comply with country-specific regulatory requirements relating to safety reporting to the regulatory authority, IRB/Independent Ethics Committees (IEC), and Investigators.
- Investigator safety reports must be prepared for suspected unexpected serious adverse reactions (SUSAR) according to local regulatory requirements and Sponsor policy and forwarded to Investigators as necessary.
- An Investigator who receives an Investigator safety report describing an SAE or other specific safety information (e.g., summary or listing of SAE) from the Sponsor will file it along with the Investigator's Brochure and will notify the IRB/IEC, if appropriate according to local requirements.

7.3.5 Pregnancy

- Details of all pregnancies in female participants after the start of study treatment and until at least 5 terminal half-lives after the last dose will be collected.
- If a pregnancy is reported, the Investigator should inform the Sponsor within 24 hours of learning of the pregnancy and should follow the procedures outlined in Appendix 4.
- Abnormal pregnancy outcomes (e.g., spontaneous abortion, fetal death, stillbirth, congenital anomalies, ectopic pregnancy) are considered to be SAEs.

7.4 Treatment of Overdose

For this study, any dose of atomoxetine hydrochloride greater than 80 mg or dronabinol greater than 10 mg more frequently than QHS will be considered an overdose.

In the event of an overdose, the Investigator should refer to the approved product label for advice on overdose and:

1. Contact the Medical Monitor immediately.
2. Closely monitor the participant for AE/SAE and laboratory abnormalities as medically indicated.
3. Obtain a plasma sample for PK analysis within 1 day from the date of the last dose of study treatment if requested by the Medical Monitor (determined on a case- by- case basis).
4. Document the quantity of the excess dose as well as the duration of the overdosing in the eCRF.

Decisions regarding dose interruptions or modifications will be made by the Investigator in consultation with the Medical Monitor based on the clinical evaluation of the participant.

7.5 Pharmacokinetics

PK parameters are not evaluated in this study.

8 Statistical Considerations

8.1 Sample Size Determination

In Apnimed studies atomoxetine alone has decreased AHI by 65% or more, and dronabinol has been reported to decrease AHI by about 50% (21). Assuming that 12 participants will complete the trial, the study will have 90% power to detect a treatment difference with baseline at a two-sided 0.05 significance level if the true difference is AHI is 12 units and the within-subject standard deviation 12. Considering an attrition rate of 25%, we will enroll 15 participants to complete the study.

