1.1 Synopsis

Protocol Title: Open-Label 4-Period Dose-Escalation Safety and Efficacy Study of AD313 in Participants With Obstructive Sleep Apnea

Sponsor Study Name.: SEED

Sponsor: Apnimed, Inc.

Rationale:

Selective norepinephrine reuptake inhibitors (SNRIs) such as atomoxetine are thought to improve obstructive sleep apnea (OSA) by increasing pharyngeal muscle stiffness and responsiveness.

Cannabinoids, including dronabinol, also have shown potential for reduction of OSA severity. The mechanism of beneficial action of dronabinol appears to be distinct from that of SNRIs, potentially involving stabilization of respiratory patterns and increased activation of upper airway dilating muscles during sleep.

The SEED study is designed to assess the safety and efficacy for OSA of 3 escalating dose combinations of atomoxetine with dronabinol, compared to baseline and to atomoxetine alone.

Overall Design:

The SEED study is an open-label, 4 consecutive period dose-escalation study of combinations of atomoxetine with dronabinol vs. atomoxetine alone in participants with moderate- to severe OSA. A screening polysomnogram (PSG) will be conducted to establish that each participant meets study enrollment criteria and to serve as baseline. Each participant will then receive escalating doses of atomoxetine, then escalating doses of the combination of atomoxetine with dronabinol, as follows:

- Week 1: atomoxetine 40 mg x 3 days, then atomoxetine 80 mg x 4 days
- Week 2: atomoxetine 40 mg/dronabinol 2.5 mg
- Week 3: atomoxetine 80 mg/dronabinol 5 mg
- Week 4: atomoxetine 80 mg/dronabinol 10 mg

Dosing of study drug occurs at the participants usual bedtime. Dose escalation will be based on safety and tolerability, as assessed at weekly clinic visits and telephone contact with participants mid-week of each dosing period.

In addition to the screening/baseline PSG, three on-drug PSGs will be conducted on the final night of the following dosing periods:

- 1st week, dosing atomoxetine 80 mg alone
- 3rd week, dosing atomoxetine 80 mg/dronabinol 5 mg
- 4th week, dosing atomoxetine 80 mg/dronabinol 10 mg

Number of Participants:

A total of 15 participants will be enrolled.

Study Duration:

The overall study duration will be up to 9 weeks, as follows:

- Screening, up to 3 weeks;
- Atomoxetine alone: 1 week
- Dronabinol dose escalation period: 3 weeks
- End of Study telephone contact: 2 weeks

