2.2.3 Biological Rationale

Atomoxetine is a pre-synaptic norepinephrine reuptake inhibitor indicated for the treatment of attention deficit hyperactivity disorder in children and adults. Dronabinol is synthetic delta-9-tetrahydrocannabinol (delta-9-THC) indicated for the treatment of anorexia in patients with AIDS and nausea and vomiting associated with cancer chemotherapy. Apnimed believes that the combination of dronabinol and atomoxetine may have an improved efficacy profile in patients with OSA compared to either constituent alone.

3 Endpoints

	Endpoints
Primary	
• AHI4%, ATO 80/DRO 10 vs. baseline
Secondary	
• AHI4%, ATO 80/DRO 10 vs. ATO 80• AHI4%, ATO 80/DRO 5 vs. baseline• AHI4%, ATO 80/DRO 5 vs. ATO 80• HB4%, ODI4%, Total time with $\text{SaO}_2 < 90\%$, Proportion of participants with $\geq 50\%$ reduction in AHI4%, HB4%, ODI4%
Exploratory	
• PGI-S• PROMIS sleep impairment• PROMIS sleep disturbance• PROMIS fatigue• AHI4%, highest dose achieved by patient (ie ATO 80/DRO 5 or ATO 80/DRO 10 vs. baseline and vs. ATO 80)• AHI3 (hypopnea scored when associated with 3% O_2 desaturation)• AHI3a (hypopnea scored when associated with 3% O_2 desaturation or arousal)• OSA endotype endpoints (Vpassive, Vactive, Muscle Compensation, Loop Gain)• PSG sleep and arousal parameters
Safety Endpoints	
• Vital signs, Spontaneous adverse events, DSST, VOLT, PVT

Abbreviations: AHI = apnea-hypopnea index; ATO = atomoxetine; DSST = digit symbol substitution test; DRO = dronabinol; HB = hypoxic burden; ODI = Oxygen Desaturation Index; OSA = obstructive sleep apnea; PROMIS = Patient Reported Outcome Measurement Information System; PGI-S = Patient Global Impression of Severity; PSG = polysomnography; PROMIS = Patient Reported Outcome Measurement Information System; PVT = psychomotor vigilance task; SaO_2 = oxygen saturation; SAQLI = Sleep Apnea Quality of Life Index; VOLT = visual object learning task

4 Study Design

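### Section 8.1 calls the SD of 12 within-subject, but its 90% power is recovered only if 12 is the SD of the change from baseline; its attrition rate also does not yield 12 completers

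*Combined protocol and SAP*

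**What the plan says.** The trial has one group, and each participant serves as his or her own control. Section 3 gives the primary endpoint as "AHI4%, ATO 80/DRO 10 vs. baseline". The Synopsis (Section 1.1) provides one recording per time point: "In addition to the screening/baseline PSG, three on-drug PSGs will be conducted on the final night of the following dosing periods". The primary comparison is therefore one on-drug night against one baseline night in the same person.

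Section 8.1 holds the whole sample-size argument. It opens with the expected effect ("In Apnimed studies atomoxetine alone has decreased AHI by 65% or more") and then states: "Assuming that 12 participants will complete the trial, the study will have 90% power". The detection target is set "at a two-sided 0.05 significance level if the true difference is AHI is 12 units and the within-subject standard deviation 12". It ends: "Considering an attrition rate of 25%, we will enroll 15 participants to complete the study".

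Section 8.1 gives no source for the 12. Sections 8.1 to 8.3 name no test or model for the primary endpoint.

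**The concern.** A within-subject SD usually means the scatter of repeated single measurements around a participant's own mean. A change from baseline is the difference of two such measurements, so its SD is larger by a factor of √2. The power of a before-and-after comparison depends on the SD of the change. The label in Section 8.1 and the figure of 90% therefore cannot both be read in their usual sense.

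This passage is the only justification for the trial size. As written, a reader cannot tell whether planned power for 12 units is about 90% or about 61%. A later study that took the 12 as a per-night SD would assume twice the variance of change. For 90% power at 12 units by paired t-test it would plan 24 completers instead of 13.

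The attrition sentence adds a second, independent mismatch: the stated loss rate does not leave the number of completers on which the power rests.

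**Working it through.** **Inputs.** From Section 8.1: n = 12 completers, difference 12 AHI units, SD 12, two-sided 0.05, stated power 90%, 15 enrolled, 25% attrition. The pairing comes from Section 3 and the Synopsis.

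**Method.** Paired t-test power from the noncentral t distribution with n − 1 df and noncentrality λ = 12 / (SD of change / √n). The documents name no test, so two alternatives were also run. One is the normal approximation, Φ(λ − 1.96). The other is a repeated-measures model with pooled error, with 2(n − 1) or 3(n − 1) df for three or four nights per participant.

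**Step 1: reproduce the 90%, taking 12 as the SD of the change.** λ = 12 / (12/√12) = 3.464.
- Paired t, 11 df: 88.3%
- Pooled error, 22 or 33 df: 91.1% or 91.9%
- Normal approximation: Φ(3.464 − 1.96) = 93.4%

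These results lie on both sides of 90%, so the stated figure is recovered to within rounding. By paired t-test, exactly 90% with 12 completers would need an SD of change of 11.66, and 13 completers give 91.1%.

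**Step 2: take the label literally, with 12 as a per-night SD.** SD of change = 12 × √2 = 16.97, so λ = 12 / (16.97/√12) = 2.449.
- Paired t, 11 df: 60.8%
- Pooled error, 22 or 33 df: 64.9% or 66.2%
- Normal approximation: Φ(2.449 − 1.96) = 68.8%

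No two-sided method tried exceeds about 69% with 12 completers. All 15 enrolled would give 72.2% by paired t-test. On this reading, 90% power with 12 completers applies to a difference of about 17.5 units, and 90% power for 12 units needs 24 completers (91.2%; 23 give 89.97%).

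**Step 3: attrition.** 15 × (1 − 0.25) = 11.25 completers. Twelve of 15 is a loss of 3/15 = 20%. Keeping 12 after a 25% loss would take 12/0.75 = 16 enrolled. With 11 completers and an SD of change of 12:
- Paired t, 10 df: 84.8%
- Pooled error, 20 or 30 df: 88.4% or 89.4%
- Normal approximation: 91.3%

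**Step 4: the larger effect that Section 8.1 cites.** The documents give no mean baseline AHI; 20 to 30 is assumed here. A 65% fall is then 0.65 × 20 = 13.0 to 0.65 × 30 = 19.5 units. With 12 completers, paired t-test power is 93% to over 99% if the SD of change is 12, and 68% to 95% if it is 16.97.

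**The case against.** The strongest reply is that nothing is miscalculated. In a single-group before-and-after design, within-subject SD is sometimes used loosely for the SD of within-participant differences. On that reading the stated power is reproduced. This largely stands. It makes the defect one of labelling, and it is why the SD-of-change reading is taken here as the likely one.

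A reader might infer two stronger conclusions, and the documents support neither.
- *The trial has only about 61% power.* That needs 12 to be a per-night SD. Nothing in the documents shows this, and the agreement in Step 1 points the other way.
- *Power is overstated at 12 completers and 13 are needed.* That holds only for an exact paired t-test, which the plan does not name. With the same inputs, the normal approximation and the pooled-error models reach 90%.

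On attrition, 12 × 1.25 = 15, so the sponsor may have inflated the number of completers by 25%. That would explain the 15. It does not make the sentence right as a loss rate, because a 25% loss from 15 still leaves 11.25. The attrition point also says nothing about what the SD means, and the two should be kept apart. The drop to 84.8% at 11 completers belongs to the paired t-test; pooled error costs less, and the normal approximation still gives 91.3%.

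Finally, a true effect well above 12 units could be well powered on either reading, as Step 4 shows. That lowers the stakes but does not settle what the 12 is.

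**Conclusion.** The point holds as a minor one. The SD label and the stated power in Section 8.1 agree only if 12 is the SD of the within-participant change from baseline. Power with 12 completers is then 88.3% by paired t-test and 91% to 93% by the other methods. Under the literal label it is 60.8% by paired t-test and at most about 69%. The mismatch rests on arithmetic and is firm. That the SD is loosely labelled is an inference from which reading reproduces the 90%, and only the source of the 12 can confirm it. The 61% is conditional and is not a finding about this trial.

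Independently, the attrition rate and the number of completers disagree: 25% of 15 leaves 11.25, while 12 completers implies 20%. On the likely reading, going from 12 to 11 completers takes paired t-test power from 88.3% to 84.8%, about 5 points below the stated 90%.

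**What to change.** Trace the source of the 12 and restate Section 8.1, keeping enrolment at 15.
- If 12 is the SD of the change from baseline, say so, name the primary test and give its power. For a two-sided paired t-test that is about 88% with 12 completers and about 85% with 11.
- Only if the source shows a per-night SD, state about 61% power for 12 units and 90% power for about 17.5 units, both by paired t-test with 12 completers. Keeping 15 enrolled then means accepting about 61% for 12 units.
- In either case, make attrition and completers agree: 20% with 12 completers, or 25% with 11.

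The cost is a check of the source, a few reworded lines in Section 8.1 and, on the likely reading with a paired t-test, a stated power about 2 points lower with 12 completers or about 5 points lower with 11. Trial procedures do not change.

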An End-of-Study phone call will take place 2 weeks following the end of study drug dosing.

Participants who discontinue from the study will not be replaced. No subsequent open-label extension is planned following the study.

Figure 1: Overview of Study Design

EoS = End of Study; PSG = polysomnography; 40 = atomoxetine 40 mg alone; 80 = atomoxetine 80 mg alone; 40/2.5 = atomoxetine 40 mg/dronabinol 2.5 mg; 80/5 = atomoxetine 80 mg/dronabinol 5 mg; 80/10 = atomoxetine 80 mg/dronabinol 10 mg

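### Section 8.1: 12 completers, 25% attrition and 15 enrolled do not agree; 15 enrolled at 25% attrition gives 11.25 expected completers (small effect)

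*Combined protocol and SAP*

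**What the plan says.** Section 8.1 states the power first: "Assuming that 12 participants will complete the trial, the study will have 90% power to detect a treatment difference with baseline". The significance level is two-sided 0.05, and the effect assumption is that "the true difference is AHI is 12 units and the within-subject standard deviation 12". The enrolment number follows: "Considering an attrition rate of 25%, we will enroll 15 participants to complete the study".

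Two other places bear on it. The synopsis (1.1) repeats the number: "A total of 15 participants will be enrolled". Section 4.1 rules out topping up: "Participants who discontinue from the study will not be replaced".

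Section 8.1 names no test, does not say whether the SD of 12 belongs to a single measurement or to the paired change, and does not define attrition.

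**The concern.** The power statement, the attrition rate and the enrolment number form one chain: completers needed, inflated for dropout, gives the number to enrol. Under the ordinary meaning of attrition, any two of the three numbers fix the third, and here they fix it at a different value from the one printed.

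Completers are the right count to look at. The primary endpoint (section 3) compares AHI4% on the highest combination dose with baseline, and that sleep study is done on the last night of week 4. Section 4.1 has participants who do not tolerate escalation stop dosing, so someone who leaves early has no value for the primary comparison. Section 8 describes no method for missing data that would bring these participants back in. At stake is whether the completer count behind the 90% is one that the plan's own assumptions can be expected to produce.

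**Working it through.** **Inputs.** Completers 12, attrition 25%, power 90%, two-sided alpha 0.05, difference 12 and SD 12 (all 8.1); enrolled 15 (8.1 and synopsis); no replacement (4.1).

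**Reproducing the plan's 15.** 12 × (1 + 0.25) = 15. This adds 25% of the completers to the completers.

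**Attrition as a share of those enrolled.**
- Expected completers: 15 × (1 − 0.25) = 11.25.
- Enrolment for 12 completers: 12 / (1 − 0.25) = 16.
- Attrition implied by 15 and 12: 3 / 15 = 20%.
- In whole people, 3 dropouts of 15 is 20% (12 complete) and 4 of 15 is 26.7% (11 complete).

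**Chance of reaching 12.** If each participant drops out independently with probability 0.25 (an assumption), at least 12 complete with probability 46% when 15 are enrolled and 63% when 16 are.

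**Power if 12 is the SD of the paired change.** The standardised difference is 12 / 12 = 1.
- Paired t-test: noncentral t with n − 1 degrees of freedom and noncentrality 1 × √n.
- Normal approximation: Φ(√n − 1.960). At n = 12 this is Φ(3.464 − 1.960) = Φ(1.504) = 93.4%.

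| Completers | Paired t-test | Normal approximation |
|---|---|---|
| 12 | 88.3% | 93.4% |
| 11.25 (interpolated) | 85.7% | 91.8% |
| 11 | 84.8% | 91.3% |

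From unrounded values, the loss relative to 12 is 2.6 to 3.5 points by t-test and 1.5 to 2.1 points by normal approximation. The smallest n reaching 90% is 13 by t-test (91.1%) and 11 by normal approximation (91.3%). By t-test, then, part of the gap below 90% exists at 12 and has nothing to do with attrition.

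Averaging t-test power over the number of completers, again with independent dropout, gives 84.5% with 15 enrolled and 87.1% with 16.

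**Power if 12 is a per-measurement SD with independent errors (an assumption).** The SD of the change is 12 × √2 = 16.97. Paired t-test power is then about 61% at 12 and 56% at 11. Only the paired-change reading comes near the stated 90%.

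**The case against.** The strongest reply is that this is too small to matter. The gap is 0.75 of an expected completer, or one enrolled participant, in a 15-person open-label study, and by normal approximation the power stays above 90% at 11. The power sentence is also conditional on 12 completing, so it is not itself made false; only the enrolment sentence conflicts. The three figures do agree if 25% was meant as an inflation on completers. And 11.25 is an expectation: 12 or more could still complete.

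Most of this stands as a statement of size. The effect is small, 90% is not lost under every method, and 12 completers remain possible. It does not remove the mismatch. Rounding does not explain it, because 12 / 0.75 is exactly 16 and 11.25 does not round to 12. Inflating on completers shows how 15 probably arose, but the plan does not declare that meaning and it is not the usual one.

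A further objection is that the question about the SD is separate from attrition. That is fair. It enters here only because a recomputed power figure needs to know which SD is meant.

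**Conclusion.** The concern holds. Taking attrition as the share of enrolled participants who leave, 12 completers, 25% and 15 enrolled cannot all be true, and nothing else in the document reconciles them. The plan's figures give 11.25 expected completers against the 12 assumed.

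The consequence is minor: less than one expected completer, and roughly 1.5 to 3.5 points of power if 12 is the SD of the paired change. The arithmetic on completers is certain. The power figures depend on the test and on the SD reading, neither of which the plan states. The point is worth correcting because the sample-size justification is inconsistent as written and the correction is nearly free.

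**What to change.** In 8.1, keep 15 enrolled and do one of the following.

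1. Keep 25% attrition, state about 11 expected completers, and recompute the power at that number with the test named. The sponsor should first confirm whether 12 is the SD of the paired change. If it is, the figure is about 85% by paired t-test or about 91% by normal approximation. If it is not, these figures do not apply, so no power figure should be printed until the SD is confirmed.
2. State 20% attrition (3 of 15) and keep 12 completers, if the sponsor can justify that rate. Under the paired-change reading, power at 12 is 88% by paired t-test or 93% by normal approximation, and the test and SD should be stated here too.

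Enrolling 16 would also make the numbers agree, but it adds a participant and a change to the synopsis, which a gap this small does not require.

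The cost of either option is an edit to the sample-size sentence in 8.1, plus the sponsor's confirmation of the SD and, for option 2, of the attrition rate. No participants are added, and visits and analyses do not change.
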